## 15. SAFETY OUTCOMES

The Total Vaccinated Cohort will be used as primary analysis cohort for all safety analyses.

### 15.1. UNSOLICITED ADVERSE EVENTS

Unsolicited AEs will be coded using the latest version of MedDRA at the time of the data transfer.

For analysis of unsolicited adverse events, all vaccinated subjects will be considered. Subjects who did not report the event will be considered as subjects without the event.

The following AE variables, as presented in the planned TLF shells, will be collected on the Adverse Event form in eSource:

- Site of AE:
  - o Non-administration site. o Administration site.
- Adverse event of special interest (AESI) within 7 days post-vaccination at Day 0 (symptoms of thrombocytopenia):
  - o Yes (available AESI terms are provided in APPENDIX 3: Adverse Events of Specific Interest (AESIs) Terms):
    - AESI term.
    - Additional AESI term. o
    - No.
- Verbatim term (diagnosis).

---

Document: CHAD3-004-EBO-Z\_Interim\_Final\_SAP\_v2\_0  
Author: PPD Version Number: 2.0 Version Date: 14JUN2017

Template No: CS\_TP\_BS016 – Revision 3  
Effective Date: 01May2012

Reference: CS\_WI\_BS005

- Start date and time.
- End date and time.
- Ongoing:
  - o Yes. o No.
- Intensity:
  - o Mild.
  - o Moderate. o Severe.
- Action taken with vaccination:
  - o Investigational product withdrawn.
  - o Dose delayed. o No action taken.
- Outcome:
  - o Recovered/Resolved.
  - o Recovered/Resolved with sequelae. o Recovering/Resolving. o Fatal. o Not recovered/not resolved. o Unknown.
- Led to study discontinuation:
  - o Yes.
  - o No.
- Serious:
  - o Yes:
    - Fatal.
    - Life-threatening.
    - Requires/prolonged hospitalisation.
    - Substantial/Permanent disability.
    - Congenital anomaly/birth defect.
    - Other.
  - o No.

The following AE variable, as presented on the planned TLFs, will be collected on the Adverse Event Relationship form in eSource:

- Relationship to study vaccine, as judged by the investigator:
  - o Yes.
  - o No.

The following laboratory variable, as presented in the planned TLFs, will be collected on the Laboratory Results form in eSource:

- Platelet counts at each relevant visit.

---

Document: CHAD3-004-EBO-Z\_Interim\_Final\_SAP\_v2\_0  
Author: PPD Version Number: 2.0 Version Date: 14JUN2017

Template No: CS\_TP\_BS016 – Revision 3  
Effective Date: 01May2012

Reference: CS\_WI\_BS005

The following AE coding variables, as presented in the planned TLF shells, are to be provided by Data Management as part of the data transfer to QuintilesIMS Biostatistics:

- Primary System Organ Class (SOC).
- Preferred Term.

Unsolicited AEs will be coded using the latest version of MedDRA at the time of the data transfer. If the AE is uncoded at the time of the analysis, the AE will be analysed as 'Uncoded'. Coded items will be presented in listings and will be used in descriptive statistics.

#### 15.1.1. DERIVATIONS

Based on the aforementioned variables, the following variables will be derived:

- Most recent vaccination (refer to Section 6.7.2: Most Recent Vaccination).
- Relative day of the most recent vaccination:
  - Calculated relative to Day 0 vaccination (refer to Section 6.1: Reference Start Date and Relative Day).
- Relative days (start and stop):
  - Calculated relative to most recent vaccination (refer to Section 6.1: Reference Start Date and Relative Day).
- Within post-vaccination reporting window flag (refer to Section 15.1.6: Adverse Event (AE) Postvaccination Reporting Window).
- Dose at onset:
  - Dose at onset will be assigned for all unsolicited AEs and is defined as the most recent dose prior to the onset of the AE:
    - Total (only applicable to SAE tables).
    - EBO-Z.
    - Nimenrix.
- Number of events will be calculated as the total number of events reported in the database per relevant category. Therefore multiple events per subject would be counted for each occurrence and not just once per subject.

Refer to APPENDIX 2: Partial Date Conventions for handling of partial dates for AEs.

#### 15.1.2. ALL UNSOLICITED ADVERSE EVENTS

The following listings are planned for presentation for Total Vaccinated Cohort:

- Unsolicited AEs.
- Serious adverse events (SAEs).

---

Document: CHAD3-004-EBO-Z\_Interim\_Final\_SAP\_v2\_0  
Author: PPD Version Number: 2.0 Version Date: 14JUN2017

Template No: CS\_TP\_BS016 – Revision 3  
Effective Date: 01May2012

Reference: CS\_WI\_BS005

- Severe (grade 3) AEs.
- Adverse events of specific interest (AESIs):
  - o All available platelet counts will also be displayed in this listing.

The following tables are planned for presentation for the Total Vaccinated Cohort:

- Overview of unsolicited AEs:
  - o Number and percentage (%) of subjects in each of the following categories:
    - Unsolicited AE.
    - Severe (grade 3) unsolicited AE.
    - Related unsolicited AE.
    - Severe (grade 3) related unsolicited AE.
    - Unsolicited AE leading to premature study withdrawal.
  - o In this table AESIs (refer to Section 15.1.4: Adverse Events Of Specific Interest (AESIs)) and \*any AEs (refer to Section 15.3: Solicited and Unsolicited Adverse Events (AEs)) will be included as well.
  - o Percentage (%) of subjects will be calculated relative to the total number of subjects in the relevant analysis cohort and sub-cohort per treatment group.
  - o A 95% confidence interval (CI) for the proportion of subjects with AEs in each category will be obtained by using the exact binomial option.
  - o Subjects with multiple events in each category are counted only once in each category.
- Incidence of unsolicited AEs:
  - o Number and percentage (%) subjects with unsolicited AEs summarised by SOC and PT.
- Incidence of unsolicited AEs by severity:
  - o Number and percentage (%) subjects with unsolicited AEs summarised by SOC, PT and severity. o This table will be repeated for related unsolicited AEs.
- Incidence of unsolicited AEs by relationship:
  - o Number and percentage (%) subjects with unsolicited AEs summarised by SOC, PT and relationship.

For all unsolicited AEs the SOC's will be sorted by descending frequency of the total number of subjects with at least one unsolicited AE in the overall category. Within each SOC, PTs will be sorted by descending frequency of the total number of subjects with at least one unsolicited AE in each category. Ties will be sorted alphabetically.

All unsolicited AE incidence tables will include AEs reported during the collection period following the vaccination at Day 0. Therefore AEs reported during the collection period following the Month 6 vaccination will be excluded from the unsolicited AE incidence tables, unless otherwise specified.

All unsolicited AE incidence tables will be repeated for the following pooling of AEs, presented per age stratum:

- AEs following the active ChAd3-EBO-Z vaccination; hence:

- o EBO-Z/MENACWY-TT subjects: Unsolicited AEs within the reporting window following Day 0 vaccination.
- o MENACWY-TT/EBO-Z subjects: Unsolicited AEs within the reporting window following Month 6 vaccination.

#### 15.1.2.1. Severity

Severity is classed as mild, moderate or severe (increasing severity) and will be obtained from the Intensity variable recorded on the Adverse Events form in eSource. If there are any missing intensities at the time of the analysis, an unknown category will be used to summarise those SOC/PTs terms.

#### 15.1.2.2. Relationship to Study Vaccine

Relationship, as indicated by the Investigator, is categorised as not related or related (increasing severity of relationship) and will be obtained from the relationship to study vaccine variable on the Adverse Event Relationship form in eSource. Missing relationships should be queried prior to the analysis transfer is made to Biostatistics. If there is any missing relationship to study vaccine at the time of the analysis, an unknown category will be used to summarise those SOC/PTs.

#### 15.1.3. UNSOLICITED AEs LEADING TO PREMATURE STUDY WITHDRAWAL

Unsolicited AEs leading to premature study withdrawal, as indicated by the investigator, will be obtained from the led to study discontinuation variable on the Adverse Events form in eSource. These AEs will be included in the unsolicited AE overview and also indicated in the unsolicited AE listing.

#### 15.1.4. ADVERSE EVENTS OF SPECIFIC INTEREST (AESIs)

Adverse events of specific interest (AESIs), as indicated by the investigator, will be obtained from the clinical symptoms of thrombocytopenia within 7 days post vaccination Day 0 variable on the Adverse Events form in eSource.

The following tables are planned for presentation for the Total Vaccinated Cohort:

- Overview of AESIs:
  - o These will be presented together with the overview of unsolicited AEs (refer to Section 15.1.2: All Unsolicited Adverse Events):
    - Any AESI.
    - Any severe (grade 3) AESI.
    - Any related AESI.
    - Any severe (grade 3) related AESI.
    - Any AESI leading to premature study withdrawal.
- Incidence of AESIs.
- Incidence of AESIs by severity.

---

Document: CHAD3-004-EBO-Z\_Interim\_Final\_SAP\_v2\_0  
Author: PPD Version Number: 2.0 Version Date: 14JUN2017

Template No: CS\_TP\_BS016 – Revision 3  
Effective Date: 01May2012

Reference: CS\_WI\_BS005

- Incidence of related AESIs by severity.
- Incidence of AESIs by relationship.

For all AESIs the SOC will be sorted by descending frequency of the total number of subjects with at least one AESI in the overall category. Within each SOC, PTs will be sorted by descending frequency of the total number of subjects with at least one AESI in each category. Ties will be sorted alphabetically.

Adverse event of specific interest (AESIs) tables will not be repeated for any pooled AESIs as AESIs are only following Day 0 vaccination and hence the MENACWY-TT/EBO-Z subjects will not have AESIs reported following Month 6 vaccination. Refer to APPENDIX 3: Adverse Events of Specific Interest (AESIs) Terms for a list of AE terms considered as AESIs.

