#### **5.4. General study aspects**

Supplementary study conduct information not mandated to be present in this protocol is provided in the accompanying manuals. The manuals provide the Investigator and the site personnel with administrative and detailed technical information that does not impact the safety of the subjects.

**5.5. Outline of study procedures****5.5.1. List of study procedures****Table 5 List of study procedures during visits to the vaccination centre (Amended 06 May 2015)**

Type of contact	Visit	Visit	Visit	Visit	Visit	Contact *	Visit	Visit	Visit	Contact *	Visit
Timepoint	Screening 	Day 0 	Day 3	Day 6	Day 30	Month 3	Month 6	Month 6 + 6 days	Month 6 + 30 days	Month 9	Month 12
Informed consent	•										
Informed assent 	•										
RDT for Malaria	•										
Malaria treatment 	•										
Inclusion/exclusion criteria 	•	•									
Demographic data	•										
Medical history 	•	•									
Physical examination (including vital signs  )	• 	• 	0	0	0		•	0	0		0
Pregnancy test 	•	• 					•				
Pre-vaccination body temperature		•					•				
Check contraindications to vaccination		0					0				
Study group and treatment name allocation 		0					0				
Vaccination		•					•				
Recording of administered treatment number		0					0				
30 minutes post-vaccination observation		0					0				
Blood sampling:											
Blood for haematology/ biochemistry	• 		•	•	•		•	•	•		•
Blood for humoral immunity		•			•		•		•		•
Blood for CMI 		•			•		•		•		•
Safety assessment:											
Record solicited AEs (day 0 to day 6)		•	•	•			•	•			
Record unsolicited AEs (day 0 to day 29)		•	•	•	•		•	•	•		
Record AEs of specific interest (clinical symptoms of thrombocytopenia)			•	•							
Record SAEs	• 	•	•	•	•	•	•	•	•	•	•
Record pregnancies		•	•	•	•	•	•	•	•		

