**9.1.5. Adverse events of specific interest****9.1.5.1. Clinical bleeding within 7 days post-vaccination at Day 0**

*In the Phase 1 studies with the investigational ChAd3-EB0-Z vaccine in healthy adults, transient decreases in thrombocyte counts were observed. These decreases occurred mostly on Day 1 after vaccination and generally returned to baseline by Day 7. Although most of these decreases remained within the normal range, the as per protocol criteria for thrombocytopenia (thrombocyte count of  $< 150 \times 10^3/\mu\text{L}$ ) were met for 2.6% (7 out of 270) of the vaccinated subjects. None of the decreases in thrombocyte counts or the cases of thrombocytopenia were clinically significant, i.e., no clinical signs or symptoms suggestive of increased tendency to bleed were reported in any of the subjects. Please refer to the IB for more information.*

*In the current study, a more vulnerable population (children) will be enrolled and the acceptable limit for the thrombocyte count for study eligibility (thrombocyte count of  $\geq 100 \times 10^3/\mu\text{L}$  is acceptable) will be lower as compared to the Phase 1 studies. In addition, in order to ensure enhanced vigilance from the Investigators, clinical bleeding events (according to the Standardised MedDRA Query clinical haemorrhage) within 7 days after vaccination at Day 0 will be recorded and reported as AEs of specific interest (clinical symptoms of thrombocytopenia).*

*(Amended 06 May 2015.)*

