#### ***Adverse events of specific interest***

***All AEs of specific interest (clinical symptoms of thrombocytopenia) starting in the 7-day follow-up period following vaccination at Day 0 must be recorded in the appropriate section of eSource.***

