## **11. STATISTICAL METHODS**

### **11.1. Primary endpoints**

- Occurrence of each solicited local and general AE, during a 7-day follow-up period after each vaccination in all subjects, in both groups.
- Occurrence of any unsolicited AE, during a 30-day follow-up period after each vaccination (*i.e.*, the day of vaccination and 29 subsequent days), in all subjects, in both groups.

- Occurrence of haematological (CBC, including differential count and platelet count) and biochemical (ALT, creatinine) laboratory abnormalities at Screening, Day 3, Day 6, Day 30, Month 6, Month 6 + 6 days, Month 6 + 30 days and Month 12 in all subjects in both groups.
- ***Occurrence of clinical symptoms of thrombocytopenia (AE of specific interest), during a 7-day follow-up period after vaccination at Day 0 (i.e., Day 0 up to Day 6), in all subjects, in both groups.***  

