### **11.8. Analysis of safety**

The analysis will be performed on the TVC.

All analyses will be descriptive. Analyses will be performed by age stratum (1 to 5 years, 6 to 12 years, 13 to 17 years) and overall.

In a first step, the safety results will be presented by treatment administered at Day 0 (ChAd3-EBO-Z vaccine [300 subjects] versus *Nimenrix* [300 subjects]). In a second step, all **available** data post-vaccination with the investigational ChAd3-EBO-Z vaccine (ChAd3-EBO-Z vaccine at Day 0 [300 subjects] and ChAd3-EBO-Z vaccine at Month 6 [300 subjects]) will be pooled (600 subjects). The latter aggregated data cannot be presented versus control because of the administration of the investigational ChAd3-EBO-Z vaccine to the children in the Group MENACWY-TT/ EBO-Z, who initially received *Nimenrix* (population overlap).

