#### 15.1.6. ADVERSE EVENT (AE) POST-VACCINATION REPORTING WINDOW

All AE incidence tables will only include AEs (SAEs, AESIs and unsolicited AEs) which occurred within the protocol defined post-vaccination reporting window, as defined in Table 5: Unsolicited Adverse Event (AE) Postvaccination Reporting Windows, below. All AE listings will include all the AEs reported, regardless whether it was reported within the reporting window. All AEs reported outside the reporting window will be indicated in the listing.

Table 5: Unsolicited Adverse Event (AE) Post-vaccination Reporting Windows

Adverse Event Type	Post-vaccination Reporting Window
SAEs	Through data cut-off
AESIs	7-day window following Day 0
Unsolicited AEs	30-day window following each vaccination

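### The bleeding AESI window follows the Day 0 visit, not the ChAd3-EBO-Z dose, so the Month 6 ChAd3-EBO-Z exposure of about 300 children gets no AESI flag and no grouped bleeding rate

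*SAP*

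**What the plan says.** Protocol 9.1.5.1 gives the reason for the endpoint. Transient platelet falls followed ChAd3-EBO-Z in Phase 1 adults, 7 of 270 (2.6%) met the thrombocytopenia criterion, and none had signs of bleeding. Because children are regarded as more vulnerable, clinical haemorrhage events "within 7 days after vaccination at Day 0 will be recorded and reported as AEs of specific interest".

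The Day 0 window is then carried through both documents:

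- Protocol 11.1 lists as a primary endpoint "Occurrence of clinical symptoms of thrombocytopenia (AE of specific interest), during a 7-day follow-up period after vaccination at Day 0", in both groups.
- Protocol 9.3.1 requires recording of AESIs "starting in the 7-day follow-up period following vaccination at Day 0 must be recorded".
- Protocol Table 5 (section 5.5.1) marks AESI recording at the Day 3 and Day 6 visits only.
- SAP v2 Table 5 (section 15.1.6) sets the AESI window as "7-day window following Day 0".
- SAP v2 15.1.4 states that AESI tables will not be repeated for pooled data, since "AESIs are only following Day 0 vaccination and hence the MENACWY-TT/EBO-Z subjects will not have AESIs reported following Month 6 vaccination".

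Group MENACWY-TT/EBO-Z receives Nimenrix at Day 0 and its single ChAd3-EBO-Z dose at Month 6 (Protocol section 3, Table 2).

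The other primary safety endpoints do reach that Month 6 dose. Solicited and unsolicited AEs are collected after each vaccination, laboratory abnormalities include Month 6 + 6 days and Month 6 + 30 days, and SAEs run throughout (Protocol 11.1). SAP v2 15.1.2, 15.2.2 and 15.4 repeat the unsolicited, solicited and most laboratory tables for all data after ChAd3-EBO-Z. Protocol 11.8 plans that pool at 600 children.

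**The concern.** The primary objective is the safety of a single ChAd3-EBO-Z dose, overall and by age stratum. The hazard belongs to that vaccine, so the natural anchor for the window is the ChAd3-EBO-Z dose. Anchoring it to Day 0 means that, in one of the two groups, the AESI window observes only Nimenrix. Neither document gives a reason.

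The platelet data fill the gap only partly. Phase 1 falls occurred mostly on Day 1 and had generally returned to baseline by Day 7. After the Month 6 dose there is no Day 3 sample; the first scheduled count is at Month 6 + 6 days. The platelet percent-decrease table in SAP v2 15.4 is also not pooled.

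At stake is precision for the one hazard singled out for closer watch. A non-serious bleed after the Month 6 dose would appear only as a row among system organ classes and preferred terms. The Appendix 3 list runs over many pages, and no summary row collects those terms for these children.

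**Working it through.** **Inputs.** Planned ChAd3-EBO-Z recipients: 300 at Day 0 and 300 at Month 6 (Protocol 11.8), or about 100 per group in each age stratum (Protocol Table 4). Precision basis: exact two-sided 95% intervals with n = 300 (Protocol Table 22). Dropout: no rate is given and withdrawals are not replaced (Protocol 10.2), so 0% to 20% loss before Month 6 is assumed. True bleeding rate in children: not given, so 0.1% to 1% is assumed.

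**Plan's own figures.** With 0 events the exact 95% upper limit is 1 − 0.025^(1/n).

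- n = 300: 1 − 0.025^(1/300) = 0.0122, as printed in Table 22. All seven rows of Table 22 reproduce to four decimals.
- Table 23, first row: 1 − (1 − 0.008)^300 = 0.910. The rate giving exactly 90% is 1 − 0.1^(1/300) = 0.0077, printed as 0.008.

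**Share of recipients without an AESI window.** No loss: 300/600 = 50%. With 20% loss: 240/(300 + 240) = 240/540 = 44%.

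**Zero-event upper limit if Month 6 doses are counted too.**

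| Population | n, Day 0 only | Upper limit | n, pooled | Upper limit |
|---|---|---|---|---|
| Overall, no loss | 300 | 1.22% | 600 | 0.61% |
| Overall, 20% loss | 300 | 1.22% | 540 | 0.68% |
| One age stratum, no loss | 100 | 3.62% | 200 | 1.83% |

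**Rate detectable with 90% probability (at least one event).** 1 − 0.1^(1/600) = 0.0038 pooled, or 0.0043 with n = 540, against 0.0077 with n = 300.

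**Chance of seeing at least one case, 1 − (1 − p)^n.**

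| Assumed true rate p | 300 doses | 600 doses |
|---|---|---|
| 0.1% | 26% | 45% |
| 0.3% | 59% | 84% |
| 0.5% | 78% | 95% |
| 1% | 95% | >99% |

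These contrasts describe the flagged, grouped endpoint. They do not mean that children are unobserved after Month 6: bleeding is still recorded then through the general AE route.

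**The case against.** The strongest reply is that this is a consistent choice with limited consequences. Protocol and SAP agree on the window. The sample-size section (Protocol 11.4) frames precision within a group before the Month 6 vaccination, so the 1.2% limit is what was planned. Pooled data have no control, and investigators know the assignment once the trial becomes single-blind at the interim analysis, so a Month 6 AESI flag would be weaker evidence than a Day 0 one. All analyses are descriptive. This stands, and it limits how serious the point is.

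It also disposes of four stronger readings that a reader might infer:

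- *The SAP contradicts Protocol 11.8.* It does not. That section pools all *available* data after ChAd3-EBO-Z, and AESIs after Month 6 are not collected. For AESIs it promises only a detailed description.
- *The control children are left out of the endpoint.* They are its randomised comparator after Day 0. Only their later ChAd3-EBO-Z exposure falls outside it.
- *Bleeding after Month 6 is lost and no pooled figure is possible.* Daily follow-up for seven days continues (Protocol 5.6.14.1), unsolicited AEs are collected for 30 days and MedDRA-coded, and SAP v2 15.1.2 pools them. A grouped count can be derived from these data.
- *Month 6 recipients have no rapid reporting.* Any SAE is reported within 24 hours throughout the study, blood dyscrasias are named as possible serious events (Protocol 9.1.2), and a related SAE triggers an ad hoc IDMC meeting. Only non-serious bleeds lack the 24-hour report.

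The reply does not explain why this endpoint alone ignores the second set of ChAd3-EBO-Z doses, or why a grouped count should be omitted when the coded data allow one.

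**Conclusion.** The point holds as a gap in design and tabulation. The AESI follows the calendar visit and not the vaccine that prompted it, which is out of line with the pooling used for the other safety endpoints. The ChAd3-EBO-Z exposure without a flag or a grouped bleeding rate is 50% of planned recipients, or 44% if 20% are lost before Month 6. Counting it would roughly halve the zero-event upper limit, from 1.2% to between 0.61% and 0.68% overall, and from 3.6% to 1.8% per age stratum with no loss.

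The gain assumes that unsolicited-AE reporting in the seven days after Month 6 picks up bleeding about as well as the flagged Day 0 process. That is plausible given daily follow-up, but it cannot be shown from the documents. The detection probabilities depend on the assumed rates. No comparison or conclusion in the plan is invalidated, so this is a should-fix and not a must-fix.

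**What to change.** **SAP 15.1.4.** Replace the no-pooling sentence with a derived table, overall and by age stratum, with exact 95% CIs:

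- Count subjects with any Appendix 3 preferred term among coded unsolicited AEs, including SAEs, with onset on Days 0 to 6 after the ChAd3-EBO-Z dose. That dose is Day 0 in Group EBO-Z/MENACWY-TT and Month 6 in Group MENACWY-TT/EBO-Z.
- Present it by group and pooled, using the same derivation in both groups.
- Show it beside the investigator-flagged Day 0 AESI table, which stays as it is.
- Footnote that Month 6 events were not flagged and were ascertained single-blind once the interim analysis had been done.
- Map Appendix 3, which is in MedDRA 17.1, to the dictionary version used for coding. State that the list includes laboratory terms such as decreased platelet count.

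**Only if Month 6 collection is still open.** Also change the AESI recording window to run after each vaccination in Protocol 9.1.5.1, 9.3.1, 11.1 and Tables 5 and 18, and in SAP Table 5. The daily follow-up and the Month 6 + 6 days visit already exist, so no visit is added.

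**Cost.** One extra table from data already planned, whose Month 6 half rests on weaker ascertainment. If collection is open, an amendment and a few more 24-hour reports.
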